25.0 Provisions to Protect the Privacy Interests of Subjects

EHR-Based Medication Complete Communication (EMC²) Strategy to Promote Safe Opioid Use: A Physician Randomized Trial

- 25.1 Only patients consenting to participate in study follow-up will be asked to interact with study personnel at future dates (follow-up calls).
- 25.2 We will also attempt to reduce shame and performance anxiety as a result of interviews about compliance with screening and assessments through extensive training of the research assistants. If any misuse of the medication is discovered during the interviews, there will be a process in-place to connect them to further medical care if required (see appendix).
- 25.3 [name] will conduct the EDW data pull to access the data elements from the medical record. The remainder of the RA staff will only access the chart if a patient had a return visit to the ED within 30 days of enrollment. In that case, a chart review of that visit will be performed by the RA. Two of the study co-Is will access the information in the Illinois Prescription Monitoring Database directly (Drs. [name] and [name]).

26.0 Compensation for Research-Related Injury

N/A

27.0 Economic Burden to Subjects

- 27.1 Patients in one study arm who receive text messages could have to pay at a maximum \$0.70-\$1.75 cents over the course of the project, assuming charges of 10-25 cents per text message received (depending on the cell phone company and receipt of 7 text messages). We believe this expense is justified because the intervention should aide in preventing misuse of the medication and the re-imbursement for study participation was created with this cost built-in.

28.0 Consent Process

- 28.1 ED Providers. We will ask providers to consent to be part of the study, which includes consenting to be randomized to one of the three study arms. We are asking for provider consent to allow any providers who are uncomfortable with the study to opt out. As noted in recruitment, providers will be informed of the nature and details of the study via email and a brief overview at a monthly business meeting. Thus they will be asked to sign a written consent to be a part of the study, which includes their consent to allow their patients to be randomized to condition, as well as their willingness to allow us to contact them for feedback via survey.

Patients. Subjects will be informed about the nature of the study by a CITI certified RA and asked to provide consent. Specifically, they will be told that depending on the doctor they see, they may be given additional

EHR-Based Medication Complete Communication (EMC²) Strategy to Promote Safe Opioid Use: A Physician Randomized Trial

educational materials and tools to help them better understand their medication. They will also be told that additional providers, including their primary physician and pharmacist, will be informed about their prescription and may provide them with additional education. Additionally they will be notified that only those contents of their medical record that are necessary to evaluate the effectiveness of the intervention will be released to the research team at Northwestern. Finally, they will be informed about the follow-up components for the study, consisting of 3 phone calls (at 2-4 days, 7-14 days and 1 month). The patients will complete a written informed consent document and will be given a copy of the consent document. See consent document. They will be informed that they may withdraw from the study at any time and given contact information for the PI and study coordinator.

Non-consenting patients. Subjects in this study are consenting to follow-up; however, as mentioned above, because of the nature of implementing the EHR-based intervention at the system level, it is possible that patients who are seen after hours (outside of RA availability) will receive the EHR components of the intervention without being approached for consent or enrolled in the study. Note, that any patient not enrolled in the study and not providing written consent will not be called to ask to participate in follow-up visits or phone calls. We believe that were a patient to see an enrolled physician and thus potentially receive the EHR-components of the intervention, that the patient would not be exposed to any additional risk as the physician-facing interventions (e.g. EHR alert) are educational and do not change the prescribing practices of the physician.

Changes to the care delivery of the ED as a result of the intervention should be perceived as an exploratory quality improvement activity, and therefore reasonable that some patients may be exposed to new, available services as part of the study. We will only examine data on outcomes that can be collected in aggregate and not from patient interviews (specifically, we will examine, via the EDW, return visits to the emergency department). There is no collection of PHI, rather a comparison of already available ED data between study arms.

Follow-up providers. The PCPs and pharmacists identified by chart review and pill bottle review during patient follow up will be asked to consent to complete a survey gauging their responses to the intervention which their patients received. These providers will be asked to document their consent by clicking an “I agree” box (on the electronic version of the survey) or by returning the survey (paper version of the survey). (See survey attachments with consent statements)

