3.0 Inclusion and Exclusion Criteria

3.1 Screening for eligibility for study

Emergency Department Providers. The research study will be described to providers by the emergency department leadership and study leadership, both via email and at in-person business meetings. All ED providers

EHR-Based Medication Complete Communication (EMC²) Strategy to Promote Safe Opioid Use: A Physician Randomized Trial

(attending MD, resident MD, NP, PA) with the exception of study investigators will be eligible. Providers will be asked to complete a written consent form if they choose to be involved in the study.

Patients. During the patient recruitment period, the RA will make frequent rounds through the ED and ask physicians to identify potentially eligible patients who will be discharged home on opioid pain relievers. The RA also will carry a pager so that physicians can notify the RA if they have an eligible patient. This method of patient identification has a well-established track record within our ED for maximizing enrollment while minimizing RA downtime. If the patient is interested in participating or learning more about the study, the RA will obtain verbal permission to ask the patient a brief series of questions to determine eligibility (see criteria below). If the patient is eligible for the study, the RA will proceed with obtaining written informed consent.

Follow-up Providers. Certain providers will interact with consented patients after the intervention takes place (e.g. Primary care physicians (PCP) and outpatient pharmacists). These providers will have no required role in carrying out the intervention (which is carried out by the EHR enhancements). These providers will be identified by chart review (PCP) and pill bottle review (pharmacists) at the time of patient follow-up. <30% of ED patients have on-staff PCP and there is no way to predict where the patients will fill their prescriptions (e.g., on-site Walgreens or another pharmacy). After identifying these providers at the time of follow-up, we will contact them via email or mail to participate in a survey. Both types of surveys will be offered to accommodate providers' busy schedules and because the pharmacists are located at diverse locations across the city of Chicago. The survey will assess the implementation of the EHR interventions and the providers' reactions to receiving additional information about their patients who were prescribed opioids in the ED.

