The initial study visit (baseline) will be conducted at the time of patient enrollment. Following this baseline interview, RAs will conduct three telephone interviews (at 2-4 days post-baseline, 7-14 days post-baseline and at one month post-baseline). The first two assessments (at enrollment and 2-4day follow-up call) have been included to closely track patient recall of counseling and knowledge, while the latter two assessments (7-14 day follow-up call and 1 month follow-up call) are included to assess decay of knowledge, safe use, storage of medications and demonstrated dosing. The final call (one month post-baseline) will assess disposal of

EHR-Based Medication Complete Communication (EMC²) Strategy to Promote Safe Opioid Use: A Physician Randomized Trial

medications and determine if patients have received additional opioid pain relievers from other providers.

Baseline Interview. At the time of enrollment, the RA will ask the participant to indicate the best days and times to call within a 2-4 day range. A \$5 Gift card given to the participant for completion of enrollment tasks.

First Study (2-4 Day) Phone Call. The study phone call will be conducted at a time of convenience for the patient, however still within a 2-4 day range post-baseline. Additionally during this phone call, the RA will either confirm or schedule the 7-14 day follow-up call. A \$10 Gift card will be mailed to the participant for completion of first phone call.

Second Study (7-14 Day) Phone Call. The second phone call will be conducted at a time of convenience for the patient, however still within 7-14 day range post-baseline. Patients will be compensated for their time to complete the call with a \$20 gift card which will be mailed to the participant upon completing the call. Patients will also be asked to mail back their de-identified medication diary using the prepaid envelope provided at baseline.

Third/Final Study (1 Month) Phone Call. The final study phone call will be conducted at a time of convenience for the patient, however still within 1-month post-baseline. (See Attached Interview script)

Intervention Patients with physicians randomized to the EMC² arm will receive the 5-part EMC2 intervention.

[figure not shown]

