[5] Finally, there will be a notification to the primary care physician (PCP) if the patient has a PCP in the Northwestern system. This notification was initially conceptualized as being automated when the inpatient and outpatient Cerner systems were compatible. Since the switch of the outpatient Northwestern Medicine offices to the EPIC EHR, this automated function is not longer available. Therefore, the RAs enrolling the subjects will note if the patient has a Northwestern Medicine physician. If the patient enrolled for follow-up has a physician in the system, the RA will manually log-in to the outpatient EPIC interface (with write functionality) and send the PCP an inbox message with the following sample text: "Your patient NAME, DOB was seen in the Northwestern Emergency Department on MONTH DATE, 20XX. They received a prescription for Hydrocodone-Acetaminophen (DOSE, TIMING, NUMBER OF TABS). When you see this patient for a follow-up appointment, please consider counseling them about the safe use of this medication. For additional information about your patient's visit to the Emergency Department, you may access the Emergency Department Note and Depart Summary. The Depart Summary will also contain a copy of the information sheet that your patient received about their new prescription pain medication."

EHR-Based Medication Complete Communication (EMC²) Strategy to Promote Safe Opioid Use: A Physician Randomized Trial

[Note: Neither the Pharmacist nor the PCP receiving the messages to “consider counseling the patient” are required to take any action as part of the intervention. The study is designed with the ED as point of care and we will be assessing implementation to gauge the response to these messages among those PCPs and pharmacist who received them; however, these providers are not required to do anything as part of the study or intervention.]

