Patients with ED physicians randomized to the EMC² +SMS Text reminder arm will receive the above-described 5 components of the EMC² intervention, and also will receive daily text reminders for one week (7 messages) following the new prescription for an opioid pain reliever (only consented patients). The premise for the 1-week timeframe is to help patients remember precautions regarding safe use during the time they are taking the medication (average ED Rx for opioids is from pilot data is 18 tabs). Furthermore, SMS text reminders that would continue indefinitely are at risk for either being ignored, irritating patients, and/or adding an unnecessary expense to patients (i.e., patient does not have an unlimited texting plan, further challenging sustainability). Messages sent early in the week will focus on topics such as safe storage and use; those sent near the end of the week will focus on topics such as disposal and pill sharing. We will schedule EMC² text messages to arrive mid-day (12:00pm to 5:00pm), based on patient preference. (See appendix for sample text messages)

9.3 Procedures to monitor safety and minimize risk.

As a part of all of the time points of follow-up, the RAs will have a checklist of potentially dangerous behaviors related to opioids and if these items are noted in the course of data collection the RAs have a set protocol to follow. (see safety protocol attached)

9.4 The drug hydrocodone-acetaminophen is the topic of the research; however it is not being used in the research—the intervention is focused on education about this medication and the study will not change the drug, dose, frequency, quantity or refills that the ED physician selects in the course of their normal clinical care.

Sources of Materials:

Electronic Health Record (EHR): Patient information and outcomes will be extracted from the EHR (demographics, ED return visits and re-admissions). Re-admissions and re-visits to the hospital and ED data will be abstracted from medical records for all patients enrolled into the study, as well as all patients prescribed an opioid during the recruitment period of 18-months.

EHR-Based Medication Complete Communication (EMC²) Strategy to Promote Safe Opioid Use: A Physician Randomized Trial

Illinois Prescription Monitoring Program (ILPMP): We will obtain data from the ILPMP on medication fill date, subsequent refills of the prescribed opioid, and new prescriptions for other controlled substances.

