18.0 Sharing of Results with Subjects

18.1 No results will be shared with subjects. Patients' primary care providers may become aware that they are enrolled in a study through an EHR-notification, however this will not contain any study results—simply a note that the patient received a prescription for Norco and was counseled about it in the ED using the MedSheet.

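### Section 28.1 has patients told without condition that their primary physician will be informed of the prescription, but the protocol provides that message for under about 20% of them

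*Protocol*

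**What the plan says.** Section 28.1, on patient consent, makes two statements in sequence. The first is conditional: "they will be told that depending on the doctor they see, they may be given additional" educational material and tools. The second is not: "They will also be told that additional providers, including their primary physician and pharmacist, will be informed about their prescription". That second sentence goes on to say that these providers may offer further education, so it treats the informing as certain and the education as possible.

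Section 9.2 lists the note to the dispensing pharmacist as component [4] of the intervention and the PCP message as component [5]. It assigns the components by arm: "Patients with physicians randomized to the EMC² arm will receive the 5-part EMC2 intervention", and those in the EMC² + SMS arm "will receive the above-described 5 components of the EMC² intervention" plus the texts. No such notice is described for usual care. Component [5] has a further limit: "there will be a notification to the primary care physician (PCP) if the patient has a PCP in the Northwestern system". Section 3.1 gives the relevant share: "<30% of ED patients have on-staff PCP". Section 18.1 is more cautious than 28.1 and says only that "primary care providers may become aware that they are enrolled in a study".

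**The concern.** Sections 28.1 and 9.2 cannot both describe what happens. A patient consented as 28.1 describes is assured that a named clinician will learn of an opioid prescription. For most patients the protocol contains no step that would bring this about.

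Two things are at stake. The first is the accuracy of consent, which matters whatever the effect on outcomes. The second is safety: a patient who believes the PCP already knows has less reason to mention the drug. Section 12.0 itself lists overdose and use with sedatives or acetaminophen among the adverse events that could occur.

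A third consequence is conceivable. H1 compares reported physician and pharmacist counselling between arms, and the sentence describes intervention content to usual-care patients, some of whom might then ask for counselling.

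**Working it through.** The documents give no figure for the share of patients whose PCP is notified, so there is none to reproduce. It follows from their own inputs.

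**Inputs**
- Patients enrolled: 1500 (section 4.1).
- Arms: three, with equal numbers of physicians (section 11.1). Equal patients per arm is an assumption; it gives 1500/3 = 500 in usual care and 1000 in the EMC² arms.
- Share with a PCP in the system: below 0.30 (section 3.1). I assume that on-staff there means in the Northwestern system in 9.2, and that the ED-wide share applies to enrollees.

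**Main calculation**
- Share notified = P(EMC² arm) × P(in-system PCP) < 2/3 × 0.30 = 0.20, or fewer than 300 of 1500.
- Share not notified > 1 − 0.20 = 0.80, or more than 1200 of 1500: 500 in usual care plus more than 1000 × 0.70 = 700 in the EMC² arms. The usual-care patients are inside the 80% and must not be added to it.

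**Sensitivity to the inputs**

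| In-system PCP | Share in EMC² arms | Notified | Not notified |
|---|---|---|---|
| 30% (ceiling) | 2/3 | 20% | 80% |
| 25% | 2/3 | 17% | 83% |
| 20% | 2/3 | 13% | 87% |
| 10% | 2/3 | 7% | 93% |
| 30% | 60% | 18% | 82% |
| 30% | 72% | 22% | 78% |

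**Sensitivity to the reading**
- Suppose the condition in the first consent sentence carries over to the second, so that the assurance concerns only patients of EMC² physicians. It still fails for over 1 − 0.30 = 70% of those patients.
- Suppose the message were sent in every arm, since the step in 9.2 where the research assistant writes to the PCP does not repeat the arm. It would still miss over 70% of all patients. This reading is unlikely: the step sits under component [5], and its sample text refers to an information sheet that the patient received.

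**How many have a PCP who is not told**

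Patients without an in-system PCP either have one elsewhere or have none, and the documents do not give the split. Let s be the in-system share and o the share with a PCP elsewhere. The share with a PCP whom the study does not notify is s/3 + o. With s at 0.30, o lies between 0 and 0.70, so the result runs from 0.10 (150 patients) to 0.80 (1200 patients).

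**The case against.** Section 28.1 is a protocol summary that refers the reader to the consent document, which was not available for this review. Section 24.1 summarises the same consent in conditional terms, so the form itself may be correct. This stands: the finding concerns the protocol's account of consent, not the form.

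A reader might infer that the pharmacist half is also untrue for usual care. The documents do not support that. The sentence speaks of the pharmacist being informed about the prescription, and a pharmacist who fills it is informed in any arm. What usual care lacks is the study's note asking the pharmacist to consider counselling.

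A reader might also take the 80% as the number of patients misled. It is not. It counts patients for whom no PCP message is provided, including any with no PCP, for whom a false belief about their own doctor cannot arise.

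Finally, a reader might infer that usual care is contaminated and H1 biased. Nothing in the documents shows that patients would act on this sentence. It is given to all arms, H1 is of secondary interest in section 11.1, and self-reported counselling is a tertiary endpoint in 8.1. The research assistants' safety checklist also operates at every follow-up contact (section 9.3), which limits the safety worry without correcting the assurance.

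None of this rescues the statement about the primary physician, which fails for most patients on every reading tried above.

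**Conclusion.** The concern holds for the primary physician. As written, section 28.1 gives an unconditional assurance that section 9.2 provides for under about 20% of patients and does not provide for at least about 80%. This rests on equal patients per arm, on the ED-wide PCP share applying to enrollees, and on the two descriptions of a Northwestern PCP meaning the same thing. Uneven arms move the figure only to 78–82% at the 30% ceiling, and a lower PCP share raises it.

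This is a matter of consent accuracy, with a plausible but unquantified safety aspect. An effect on the H1 contrast is possible and unproven. Sample size, allocation and the analysis model are unaffected.

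**What to change.** Reconcile section 28.1 with sections 3.1, 9.2 and 18.1 by making the sentence conditional and using the same words in every arm. For example: *depending on the doctor you see and whether your primary doctor is in the Northwestern system, your primary doctor and pharmacist may be sent a note about this prescription*. Then check the consent form, and any script used by the research assistants, against it.

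Do not add an instruction telling patients not to assume that their doctors know. It goes beyond what consistency requires and would itself be a new counselling message to usual care.

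The cost is a minor amendment to one sentence. The SAP, dated June 2019, describes its analyses in the past tense, so enrolment may well have closed. In that case the wording patients actually received should be reported alongside the counselling results, which costs a sentence in the report.

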29.0 Process to Document Consent in Writing

29.1 ED physicians being randomized to study arms

EHR-Based Medication Complete Communication (EMC²) Strategy to Promote Safe Opioid Use: A Physician Randomized Trial

Written informed consent will be obtained from ED physicians (both attending and resident physicians). All participants will be told that their participation is voluntary; they can stop at any time, and whether they participated or not will not be disclosed to their superiors. Their participation in the EHR-based intervention will be kept confidential and made anonymous in reports. If the physician does not want to participate or decides to stop before completing the 18-month patient enrollment period, this will not be disclosed to any superiors.

Patients

The intervention is implemented at the physician level. Therefore patients will be recruited for follow-up purposes only, rather than for consent to the EHR portion of the intervention. For patients consenting to follow-up, the consent will be documented in writing.

For those patients receiving the intervention on the basis of having a consented provider, but not approached or consented for follow-up, we request a *waiver of informed consent* because: 1) this is a low-risk study, in particular, it is research designed to evaluate an educational strategy, 2) it would not be feasible to conduct the study as intended if obtaining individual informed consent were necessary (in this case because patients do not become eligible until a prescription is written for an opioid—but a key component of the intervention is the text on the prescription), 3) informed consent from each participant would threaten the scientific validity of the study (in this case it would be impossible to evaluate real-world dissemination and implementation of the intervention if the EHR automations needed to be turned on and off at the individual patient level) and 4) for the patients receiving the intervention, but not completing follow-up, no patient data are collected that would not be routinely collected in usual care without consent. Specifically, the only data that will be accessed on this sample of patients is demographic data from the electronic medical record and data on return visits to the emergency department and re-admission to the hospital for problems related to pain and/or opioid use.

As detailed above, this specific strategy of “turning on” an EHR intervention with physician or clinic level randomization has been previously approved by the IRB at Northwestern University for three other AHRQ funded grants (P01HS021141-01, 1U19HS021093-01 & 1R18HS017220-01).

Follow-up providers. Follow-up providers will document their consent to completing the survey as detailed above: by clicking an “I agree” button (electronic version of survey) or returning the survey (paper version of the survey).

